10.1.3 Recording and Reporting of Serious Adverse Events

Every SAE (regardless of severity and causality) that occurs once the caregiver/patient has signed the ICF and until the post-treatment follow-up (Visit 12), and 28 days after the final dose of study drug, should immediately and not later than within 24 hours of knowledge of the event, be reported by the investigator or delegate in the SAE Report Form.

Report of a SAE must include at least the following information:

- Patient identification information (study number, site number, initials, and date of birth [as per local country requirements for data protection])
- The last study drug administration date
- The diagnosis of the event with the description (or a brief description of signs/symptoms/clinical course if the diagnosis is not available) and the date of onset
- The action used to treat the event (i.e., treatment medications, temporary discontinuation)
- The reason(s) for considering the event serious
- The relationship of the event to the study drug or to the study procedure (e.g., the investigator's assessment of causality)
- A brief narrative of the SAE

Follow-up reports including all new information obtained of the subsequent course of the SAE must be prepared and the information collected in the SAE Report Form submitted to ICON

DRUG SAFETY (Pharmacovigilance and Safety Services Department) by e-mail within 24 hours of knowledge of the event.

The pharmacovigilance manager (PVM) may contact the investigator to obtain further information on a reported SAE. The investigator/investigative staff must respond to any request for follow-up information or answers to questions regarding the SAE within the same timelines as for initial reports.

The PVM reports the occurrence of the SAE and follow-up to the Albireo Medical Monitor for medical assessment of the case.

Should an outcome of death occur within the study period or within 28 days after the last administration of study drug, an SAE Report Form should be completed including the main and contributory causes of death.

All SAE reports must be e-mailed to the following e-mail address within **24 hours**:

ICON DRUG SAFETY (Pharmacovigilance and Safety Services Department)

E-mail: PPD

If email is unavailable, SAEs may be transmitted via fax to the following number:

Fax No.: PPD

In a study-related medical emergency situation, when the assigned Medical Monitors for the study cannot be reached by a caller, an on-call physician can be reached 24 hours per day, 7 days per week, via the ICON call center. The following number is a chargeable telephone number allowing a global reach from both landlines and mobile phones and the internet page indicated below contains a list of country-specific toll-free telephone numbers. It should be noted that not all countries globally have access to toll-free numbers as indicated on the “24/7 Medical Help desk” index. Countries without toll-free numbers need to dial the chargeable number as indicated below. Furthermore, toll-free numbers might not be available from mobile phones.

On Call Telephone No.: PPD

<https://icophone.iconplc.com>

10.1.4 Reporting of Suspected Unexpected Serious Adverse Reactions

Suspected unexpected serious adverse reaction (SUSAR) is an SAE that occurs in a patient, the nature or severity of which is not expected per the applicable product information (e.g., the IB for an unauthorized investigational product or summary of product characteristics for an authorized product).

Reporting and tracking of SUSARs will be in accordance with all applicable competent authority regulations. The Ethics Committees and all investigators involved in this study will be informed according to national and international requirements.

10.2 Laboratory Values/Vital Signs/Physical Examinations and Other Safety Assessments

10.2.1 Laboratory Assessments

At the clinic visits indicated in [Table 1](#), samples will be drawn for clinical chemistry, hematology, and urinalysis analyses. The parameters assessed are presented in [Table 4](#).

Blood for AFP will be drawn at Visits 1, 5, 8, and 11. Fat-soluble vitamin levels including vitamins A and E, and 25-hydroxy vitamin D will be assessed at Visits 1, 3, 4, 6, 7, 9, 10, and all optional extension period visits and INR (surrogate for vitamin K) will be assessed at Visits S-2 (Cohort 2 only), 2, 3, 4, 6, 7, 9, 10, and 12, and all optional extension period visits. Patients will fast (water intake only is permissible) for at least 4 hours prior to the collection of samples for vitamin A. Exceptions can be made for infants, <12 months of age, if unable to fast for the full 4 hours. If a patient has any vitamin level(s) that are outside of the reference range, vitamin supplementation adjustments may be required. Target ranges and supplementation strategy guidelines can be found in [Appendix 5](#).

A serum pregnancy test will be performed at Visits S-1 (Cohort 2) and Visit 1 (Cohort 1), and a urine pregnancy test will be collected at all other visits, including the optional extension period visits, for girls who have reached menarche. If a urine pregnancy test is positive, a serum pregnancy test should be performed to confirm the pregnancy. Study drug administration will be held pending the confirmatory results. If the serum pregnancy test is negative, the patient can resume dosing. If the serum pregnancy test is positive, the patient should be discontinued (see [Section 10.2.9](#)).

All samples will be processed and transported to a laboratory per instructions in the laboratory manual.

The observed values will be recorded and assessed as “normal” or “abnormal not clinically significant” or “abnormal clinically significant”.

For hepatic adverse events and/or hepatic decompensation, a PK sample should be collected as close to the onset of the event as possible (PK samples are not required during the screening period).

Additional safety blood samples may be needed due to follow-up of an abnormal value or analysis failure. The blood samples collected for safety laboratory analysis will be destroyed after the analyses have been completed.

Table 4 Routine Laboratory Parameters

Clinical Chemistry	Hematology	Urinalysis

 • Albumin* • ALT* • Alkaline phosphatase* • AST* • Bilirubin – total and conjugated* • Calcium • Chloride • Creatinine • Creatine kinase • GGT • Potassium • Sodium 
* Clinical chemistry for optional extension period
	
 • Hematocrit • Hemoglobin • Platelet count • Red blood cell count • White blood cell count and differential (neutrophils, eosinophils, basophils, lymphocytes, and monocytes) 	
 • Blood • Glucose • Ketones • Leukocytes • Nitrites • pH • Protein

10.2.2 Individual Patient Safety Monitoring

10.2.2.1 Liver Monitoring

Strategies to monitor markers of liver disease throughout the study are outlined below where the ULN will be based on central laboratory reference values for age and gender.

For abnormalities classified as hepatic adverse events and/or hepatic decompensation, a PK sample should be collected as close to the onset of the event as possible (PK samples are not required during the screening period).

If isolated transaminase elevations are observed, defined as:

1. Normal bilirubin AND absence of clinical hepatitis symptoms AND
 - ALT or AST $\geq 5 \times$ ULN (if normal at baseline) or an absolute threshold of 800 U/L, whichever comes first
 - OR ALT or AST $\geq 3 \times$ baseline (if abnormal at baseline) or an absolute threshold of 800 U/L, whichever comes first

Then:

- a) Repeat liver profile (AST, ALT, bilirubin, and prothrombin time [PT] or INR) within 2 to 3 days
- b) Evaluate creatine phosphokinase (CPK) and lactate dehydrogenase (LDH)
- c) As needed (for example, persistent ALT/total bilirubin elevation or worsening of liver function), consider evaluation for alternative etiologies

Monitor the patient using close observation found in [Section 10.2.2.2](#).

If any ONE of the following criteria are met:

1. Transaminases (ALT or AST $\geq 3 \times$ baseline or absolute threshold increase of +300 U/L, whichever comes first) AND bilirubin increases to such where total bilirubin $> 2 \times$ ULN if total bilirubin was within normal range at baseline
2. Transaminase elevations alone (ALT or AST $> 5 \times$ ULN for patients that were normal at baseline) or absolute threshold of +300 U/L (for patients starting with transaminases above ULN at baseline) in presence of normal LDH and CPK
3. Total bilirubin increased, unrelated to hemolysis (elevated reticulocyte count) or established genetic diseases, such as Gilbert's syndrome
 - a) Doubling if total bilirubin was < 3 mg/dL (equivalent to 51.3 μ mol/L) at baseline and total bilirubin is greater than 2 x ULN
 - b) OR Increase by > 3 mg/dL (equivalent to 51.3 μ mol/L) if total bilirubin was ≥ 3 mg/dL (equivalent to 51.3 μ mol/L) at baseline
4. INR increase refractory to vitamin K administration
 - a) Increase by > 1.5 if INR was normal at baseline
 - b) OR Increase by > 0.4 if INR was abnormal at baseline
5. Any increase in total bilirubin and transaminases if accompanied by EITHER a symptom of clinical hepatitis (e.g., vomiting, nausea, right upper quadrant pain) OR immunological reaction (rash or $> 5\%$ eosinophilia)

Then:

- a) Interrupt study medication
- b) Initiate drug-induced liver injury work-up for alternative etiologies
- c) Repeat liver profile (AST, ALT, total bilirubin, direct bilirubin) and PT or INR within 48 to 72 hours
- d) Monitor the patient using close observation found in Section 10.2.2.2
- e) If a patient lives in a remote area, they may be tested locally and the results communicated to the investigator site promptly

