10.2.2.2 Close Observation

- Repeat liver enzyme and serum bilirubin tests two or three times weekly. Frequency of re-testing can decrease to once a week or less if abnormalities stabilize or the trial drug has been discontinued and the patient is asymptomatic
- Obtain a more detailed history of symptoms and prior or concurrent diseases

- Obtain a history of concomitant drug use (including non-prescription medications and herbal and dietary supplement preparations), alcohol use, recreational drug use, and special diets
- Consider ruling out alternate etiology including acute viral hepatitis types A, B, C, D, and E; autoimmune or alcoholic hepatitis; non-alcoholic steatohepatitis; hypoxic/ischemic hepatopathy; and biliary tract disease
- Obtain a history of exposure to environmental chemical agents
- Obtain additional tests to evaluate liver function, as appropriate (e.g., INR, direct bilirubin)
- Consider gastroenterology or hepatology consultations
- Follow subjects with potential drug-induced liver injury (DILI) until the laboratory, and new associated clinical abnormalities have normalized or returned to baseline (enrollment) values or have stabilized (defined as laboratory values being stable for 3 months). Continue to work up for alternate etiologies for the abnormal liver disease as stated above until case has resolved. If imaging changes are found as part of the assessment for etiology, these should be continued to be followed until normalization or returned to baseline or until the investigator feels the changes have stabilized.

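### The liver observation tier applies only while bilirubin is normal, so a child with a threefold transaminase rise and moderately abnormal bilirubin can fall outside every liver rule

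*Protocol*

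**What the plan says.** Protocol section 10.2.2.1 defines isolated transaminase elevation by three joint conditions. The first two are "Normal bilirubin AND absence of clinical hepatitis symptoms AND". The third is a transaminase threshold: for a patient already abnormal at baseline, ALT or AST at 3 × baseline or more, or 800 U/L. Meeting all three requires a repeat liver profile in 2 to 3 days, the step "Evaluate creatine phosphokinase (CPK) and lactate dehydrogenase (LDH)", and close observation under section 10.2.2.2 ("Repeat liver enzyme and serum bilirubin tests two or three times weekly").

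The second tier interrupts study drug if any one of five criteria is met:

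1. ALT or AST at 3 × baseline or up by 300 U/L, together with bilirubin above 2 × "ULN if total bilirubin was within normal range at baseline".
2. For raised baseline transaminases, a rise of 300 U/L. The text reads "for patients starting with transaminases above ULN at baseline) in presence of normal LDH and CPK".
3. Bilirubin doubled and above 2 × ULN (baseline below 3 mg/dL), or up by more than 3 mg/dL (baseline 3 mg/dL or higher).
4. An INR rise that does not respond to vitamin K.
5. Any rise in bilirubin and transaminases with hepatitis symptoms, rash or eosinophilia.

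The routine chemistry panel in Table 4 (section 10.2.1) includes "Creatine kinase • GGT • Potassium • Sodium" but not LDH.

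**The concern.** The two tiers do not meet. Once bilirubin is abnormal, observation is closed, and a patient without symptoms has only the interruption criteria, which are set higher. A combined rise in transaminases and bilirubin can therefore carry less mandatory follow-up than the same transaminase rise alone.

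The situation is to be expected here. Section 5.2.1 describes PFIC biochemistry as raised bilirubin with raised ALT and AST. Cohort 2 excludes only total bilirubin above 10 × ULN (section 7.2.2). Section 5.2.2 names rises in ALT, AST and bilirubin as the most common drug-related events in children.

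LDH adds to the problem. Criterion 2 needs a normal LDH, yet the only instruction in this section to measure LDH is inside the observation tier, which this patient cannot enter.

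The remaining safeguards are discretionary or slower. Section 10.2.1 says "Additional safety blood samples may be needed due to follow-up of an abnormal value or analysis failure" and has each value classed for clinical significance. Telephone contacts for adverse events fall between visits, and the DSMB meets about quarterly.

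**Working it through.** **Inputs.** The thresholds are those of section 10.2.2.1. The protocol gives no ULN values (central laboratory, by age and gender), so the check assumes an ALT ULN of 30, 40 or 55 U/L and a bilirubin ULN of 1.0 or 1.2 mg/dL; the results below are the same for all of them. The patient has no symptoms, rash or eosinophilia (criterion 5 not met) and a stable INR (criterion 4 not met). LDH and CPK are normal unless stated. PFIC is not treated as a genetic disease that exempts a bilirubin rise under criterion 3.

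**Four patients with the same ALT course, 60 to 240 U/L.** Ratio 240/60 = 4.0; rise 240 − 60 = 180, below 300, so criterion 2 is not met in any of them.

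| | Bilirubin (mg/dL) | Observation | Criterion 1 | Criterion 3 | Result |
|---|---|---|---|---|---|
| A | 5.0 to 6.5 | no, bilirubin abnormal | no on the literal text, baseline not normal | no, +1.5 is not >3 | no tier |
| B | 0.8 to 1.8 | no, 1.8 is above ULN | no, 1.8 is not above 2.0 to 2.4 | no, 1.8/0.8 = 2.25 but not >2 × ULN | no tier |
| C | 0.6 to 0.7 | yes | no | no | observation |
| D | 0.8 to 2.6 | no | yes, 2.6 > 2.4 | yes, 2.6/0.8 = 3.25 and >2 × ULN | interruption |

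Patient B lies between C and D in bilirubin and is the one with no required action.

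**Dependence on criterion 1.** Its wording sets no bilirubin limit when baseline bilirubin is raised. If the bilirubin part falls away for such patients, or any increase is enough, A is interrupted. B has a normal baseline, so B is uncovered on every reading.

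**Width of the gap, LDH and CPK normal.** For a raised baseline B, the observation threshold is 3B and criterion 2 starts at B + 300. The gap exists when 3B < B + 300, that is B < 150 U/L, and its width is 300 − 2B.

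| Baseline (U/L) | Uncovered band (U/L) | Width |
|---|---|---|
| 60 | 180 to <360 | 180 |
| 80 | 240 to <380 | 140 |
| 100 | 300 to <400 | 100 |
| 120 | 360 to <420 | 60 |
| 150 | closed | 0 |

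The same holds for AST.

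**LDH or CPK abnormal.** Criterion 2 then cannot apply and the band has no upper end. ALT 100 to 700 U/L with bilirubin 5.0 to 6.5 meets no tier on the literal text. ALT 200 to 600 U/L with bilirubin 1.0 to 1.8 meets none on any reading of criterion 1.

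**Time to the next scheduled ALT, AST and bilirubin (Tables 1 and 2).** Chemistry falls on Days 1, 28, 84, 168, 252, 336, 420, 504 and 532. The intervals are 28 days, 56 days, then 84 days after each of Weeks 12, 24, 36, 48 and 60, and 28 days after Week 72 for those who stop. In the extension the interval is 16 × 7 = 112 days. The visits at Weeks 22, 46 and 70 come 70 days after Weeks 12, 36 and 60 (for example 154 − 84 = 70) and include INR ("INR (surrogate for vitamin K) will be assessed at Visits S-2 (Cohort 2 only), 2, 3, 4, 6, 7, 9, 10, and 12") but no chemistry.

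**The case against.** **The bilirubin condition could mean baseline bilirubin.** Patient B would then enter observation. But the same definition says explicitly when it means baseline, in both transaminase lines, and does not say so for bilirubin. Under a heading about isolated elevations, current bilirubin is the natural meaning. Patient A would be excluded either way.

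**The second transaminase line could stand alone after its OR.** That would close the gap, but it would also drop the no-symptoms condition and contradict the heading.

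**The case most typical of the disease, A, depends on how criterion 1 is read.** This is right, and the claim for A is limited to the literal text. B does not share that weakness.

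**The gap is bounded and its frequency unknown.** Also right when LDH and CPK are normal: baselines under 150 U/L, and the bands tabulated lie below 420 U/L. In the first 12 weeks chemistry is more frequent, investigators may arrange extra visits, and section 5.2.2 reports no serious event judged drug-related. These points limit the severity. They do not supply a 2 to 3 day retest that the protocol requires for the lower-risk patient C.

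**The remedy does not close every gap in the section.** This stands. ALT 200 to 510 U/L is +310 but only 2.55 × baseline, so observation is not triggered and LDH is still not ordered. A patient with nausea, ALT 60 to 240 and unchanged bilirubin meets neither tier, because criterion 5 also needs a bilirubin rise. Both are separate from the asymptomatic gap described here.

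**Conclusion.** The concern holds. As written, an asymptomatic patient with abnormal bilirubin can reach 3 × a raised transaminase baseline and meet neither tier. For bilirubin newly raised to no more than 2 × ULN this is so on every reading of criterion 1. For bilirubin raised at baseline it is so on the literal text. The size is a band of 300 − 2B U/L for raised baselines below 150 U/L, with no upper end if LDH or CPK is abnormal, and up to 84 days to the next scheduled chemistry in the main period (112 in the extension). The worked cases rest on the assumed ULNs and a stable INR; the band formula needs only that the baseline is above ULN. The number of patients affected is unknown. This should be fixed: the rule is inverted across bilirubin levels, and the correction is cheap.

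**What to change.** In section 10.2.2.1, replace the opening condition of the observation tier with: *no interruption criterion met on the results available, and no symptoms of clinical hepatitis*. Keep the transaminase thresholds. An asymptomatic patient at a transaminase threshold then either meets an interruption criterion or enters observation, so none is left without a tier. Patients A and B enter observation, and LDH is ordered for them. Judging entry on available results avoids waiting for LDH: if it returns normal and the rise is 300 U/L or more, criterion 2 then applies. The heading should be adjusted, since the elevation need no longer be isolated.

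Optionally, state how criterion 1 works when baseline bilirubin is raised; any threshold is a clinical decision for the sponsor.

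The cost is additional retests and, for some children, close-observation sampling that starts at two or three times weekly and can fall to once a week or less when values stabilise. The main change adds no scheduled visit and no interruption criterion.

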6. Any patient with suspected or confirmed cancers except for basal cell carcinoma, and non-liver cancers treated at least 5 years prior to Screening with no evidence of recurrence.
7. Patient has had a liver transplant, or a liver transplant is planned within 6 months of the Screening/Inclusion Visit.
8. Decompensated liver disease, coagulopathy, history, or presence of clinically significant ascites, variceal hemorrhage, and/or encephalopathy.
9. INR >1.4 (the patient may be treated with Vitamin K intravenously, and if INR is \leq 1.4 at resampling the patient may be included).
10. Serum ALT $>10 \times$ upper limit of normal (ULN) at Screening.
11. Serum ALT $>15 \times$ ULN at any time point during the last 6 months unless an alternate etiology was confirmed for the elevation.
12. Total bilirubin $>10 \times$ ULN at Screening.
13. Patient suffers from uncontrolled, recalcitrant pruritic condition other than PFIC. Examples include, but not limited to, refractory atopic dermatitis or other primary pruritic skin diseases.

14. Any patient who is pregnant or lactating or who is planning to become pregnant within 72 weeks of the Screening/Inclusion Visit.
15. Sexually active males and females who are not using a reliable contraceptive method with $\leq 1\%$ failure rate (such as hormonal contraception, intrauterine device, or complete abstinence) throughout the duration of the study and 90 days thereafter (from signed informed consent through 90 days after last dose of study drug). See [Appendix 6](#) for further details.
16. Patient with a past medical history of alcohol or substance abuse will be excluded. Patient must agree to refrain from illicit drug and alcohol use during the study.
17. Administration of bile acid or lipid binding resins and medications that slow GI motility (Refer to [Appendix 1](#) – Concomitant Medications Guidelines).
18. Patient has had investigational exposure to a drug, biologic agent, or medical device within 30 days prior to Screening, or 5 half-lives of the study agent, whichever is longer.
19. Any other conditions or abnormalities which, in the opinion of the investigator or Medical Monitor, may compromise the safety of the patient, or interfere with the patient participating in or completing the study.

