7.2.3 Withdrawal of Patients

Patients/caregivers will be informed that they have the right to withdraw from the study at any time, without prejudice to their medical care, and that they are not obliged to state their reasons.

Any withdrawal, and reasons for withdrawal, must be fully documented in the eCRF and source documents and the patient followed by the investigator/investigative staff. Withdrawn patients will not be replaced.

Patients will be withdrawn in the following circumstances:

- A patient's/caregiver's desire for withdrawal for any reason
- Lost to follow-up (every effort must be made to contact the patient/caregiver; a certified letter must be sent)
- An AE which, in the opinion of the investigator, necessitates withdrawal
- Death
- A patient's/caregiver's substantial non-compliance (eDiary and study drug compliance) or protocol violation
- An investigator's opinion that continuing the patient in the study is not appropriate. The investigator may withdraw a patient at any time, if it is considered to be in the patient's best interest
- Liver transplantation

The reason and the date the patient is withdrawn from the study will be documented in the eCRF and source documents. If a patient is withdrawn from further treatment with the study drug, the investigator/investigative staff will attempt to complete all Visit 11 procedures at the time the patient is prematurely withdrawn from the study. The investigator/investigative staff will also attempt to complete all Visit 12 procedures 28 days following premature withdrawal (i.e., 28 days following the final dose of the study drug).

If a patient discontinues prior to Week 72, additional telephone contacts will be made every 3 months after the Follow-up Visit (Visit 12) up to Week 72 to gather whether or not the patient has had biliary diversion or liver transplantation, and of ongoing TEAEs at the time of discontinuation have resolved. The telephone calls will take place up until 72 weeks even if the patient has biliary diversion or liver transplant.

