10.2.2.7 Re-challenge after Discontinuation/Interruption of Study Drug

The DSMB will evaluate the safety data for patients who have discontinued study drug for an extended period on a case-by-case basis to determine whether re-challenge with A4250 is appropriate. The minimal duration of the discontinuation should be at least one to two weeks.

Patients that have discontinued for an extended period and allowed re-challenge by DSMB will use the last labs prior to restart as the new baseline for determining if DILI criteria are met.

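### The INR stopping rule is stricter on children who start abnormal by a full 1.1 INR units, so a child with a normal baseline can deteriorate further, to the same INR, without criterion 4 stopping drug

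*Protocol*

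**What the plan says.** Section 10.2.2.1 (Liver Monitoring) lists five criteria, any one of which leads to interruption of study drug. Criterion 4 covers "INR increase refractory to vitamin K administration" and has two limbs:

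- 4a: "Increase by > 1.5 if INR was normal at baseline"
- 4b: "Increase by > 0.4 if INR was abnormal at baseline"

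Both limbs are increments from baseline. Meeting a criterion also sets off further steps, including "Initiate drug-induced liver injury work-up for alternative etiologies" and a repeat liver profile with PT or INR within 48 to 72 hours. The section gives no numeric normal limit for INR; limits are those of the central laboratory for age and gender.

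The protocol uses INR levels in three other relevant places:

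- Section 7.2.2 keeps a patient out of Cohort 2 for "INR >1.4 (the patient may be treated with Vitamin K intravenously", with entry possible if the resampled value is 1.4 or lower. Cohort 1 has no numeric INR limit.
- Appendix 5 sets a vitamin K target of INR 1.2 or lower and reserves its highest dosing tier for INR above 1.8.
- Under section 10.2.2.7, patients allowed to restart after an extended stop "will use the last labs prior to restart as the new baseline for determining if DILI criteria are met", so the baseline for criterion 4 can be reset.

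**The concern.** Children who start with an abnormal INR have less reserve, so a smaller allowed increment for them is defensible. The difficulty is the size of the difference and where it falls. Two children whose baselines lie just either side of the normal limit are almost identical clinically, yet one is stopped 1.1 INR units earlier than the other. The result is perverse: at the same INR, the child who has deteriorated more can be the one kept on drug. Nothing in the protocol explains or reconciles this.

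What is at stake is hepatic safety in a paediatric population. If criterion 4 is not met and the INR rise is isolated, the protocol does not require interruption, the liver-injury work-up or the 48-to-72-hour repeat. Scheduled INR draws are at Weeks 4, 12, 22, 36, 46, 60, 70 and 76. Without a triggered repeat, the next scheduled value can therefore be 14 weeks away (Weeks 22 to 36 and 46 to 60), or 16 weeks in the extension period.

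**Working it through.** **Inputs.** From section 10.2.2.1: required rise above 1.5 (normal baseline) and above 0.4 (abnormal baseline). From section 7.2.2: Cohort 2 entry cap 1.4. From Appendix 5: vitamin K target 1.2, used here as an assumed normal limit. Assumed: lowest normal baseline 0.9.

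**Formula.** Stop level = baseline INR + required rise.

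**Step at the normal limit L.** Just inside it is L + 1.5; just outside it is L + 0.4. The difference is 1.5 − 0.4 = 1.1 for every L:

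| L | 4a at L | 4b just above L | Drop |
|---|---|---|---|
| 1.0 | >2.5 | >1.4 | 1.1 |
| 1.1 | >2.6 | >1.5 | 1.1 |
| 1.2 | >2.7 | >1.6 | 1.1 |
| 1.3 | >2.8 | >1.7 | 1.1 |
| 1.4 | >2.9 | >1.8 | 1.1 |

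**Two children at a refractory INR of 2.0.** Baseline 1.3, abnormal: rise 2.0 − 1.3 = 0.7, more than 0.4, so drug is stopped. Baseline 1.0, normal: rise 2.0 − 1.0 = 1.0, not more than 1.5, so criterion 4 does not stop drug. This holds for any L from 1.0 to below 1.3.

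**Ranges, taking L = 1.2.**

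- 4a: 0.9 + 1.5 = 2.4 to 1.2 + 1.5 = 2.7.
- 4b: 1.21 + 0.4 = 1.61 to 1.4 + 0.4 = 1.80.
- Above 1.80 and up to 2.40, criterion 4 stops every abnormal-baseline patient and no normal-baseline patient. That band lies entirely in Appendix 5's top vitamin K tier, and 1.80 − 1.4 = 0.4 to 2.40 − 1.4 = 1.0 above the Cohort 2 entry cap.
- With L = 1.1, 4a is 2.4 to 2.6, 4b is 1.11 + 0.4 = 1.51 to 1.80, and the band is unchanged.
- For 4b to stop as late as 4a, its baseline would have to be 2.4 − 0.4 = 2.0 to 2.7 − 0.4 = 2.3. That is above the Cohort 2 cap, though a baseline reset at re-challenge might reach it.

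**Comparison with the other stop criteria that have baseline limbs.**

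- Criterion 3 (bilirubin) joins up. "Doubling if total bilirubin was < 3 mg/dL" gives 2 × 2.99 = 5.98 mg/dL just below the cut, and a rise of 3 from 3.0 gives 6.0 mg/dL at it.
- Criterion 2 (transaminases) steps upward. At an assumed ULN of 40 U/L, 5 × 40 = 200 U/L from a normal baseline, against about 40 + 300 = 340 U/L just above the ULN.
- Only criterion 4 steps downward.

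**The case against.** The strongest reply is that the protocol states one pair of thresholds and contradicts itself nowhere. That 4a was meant to be something else is inference. Continuity across the normal limit is not a principle the section follows throughout: criterion 2 jumps upward, and the separate isolated-transaminase rule steps down, from 5 × ULN to 3 × baseline. All of that is correct. However, the upward jump does not produce the perverse ordering, and the isolated-transaminase rule triggers monitoring rather than a stop and carries an 800 U/L cap. Criterion 4 has no absolute cap.

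The second reply is that a child at INR 2.0 is not left unmanaged:

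- Appendix 5 already calls for intramuscular plus daily oral vitamin K.
- Section 10.2.2.4 has any sign of bleeding prompt coagulation tests.
- Section 10.2.2.5 stops treatment for end-organ damage from vitamin deficiency.
- Section 10.2.1 has laboratory values graded for clinical significance and allows extra safety samples.
- The DSMB meets about quarterly.
- Section 7.2.3 says "The investigator may withdraw a patient at any time" where that is in the patient's best interest.

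These soften the problem without closing it. They are discretionary, wait for bleeding or organ damage, or supply the vitamin K to which this rise has by definition not responded. DSMB review also ends when the last patient completes 72 weeks, while dosing may continue.

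Two further points stand. The affected case is narrow: normal baseline, a rise persisting after vitamin K, and no qualifying transaminase, bilirubin or symptom change. Its frequency cannot be estimated from the document. The absolute stop levels also rest on an assumed normal range; only the 1.1-unit step does not.

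**Conclusion.** The concern holds. As written, criterion 4's stop level falls by 1.1 INR units as baseline crosses the normal limit, whatever that limit is, and no other numeric stop covers an isolated vitamin-K-refractory rise in a child who started normal. On the stated assumptions (normal 0.9–1.2, abnormal 1.21–1.4, the 1.4 cap applying to Cohort 2 only), the range of refractory INR in which the two groups are treated in opposite ways is above 1.80 to 2.40. Whether 4a is a drafting slip or a deliberate choice cannot be settled from the protocol. Either way, following it gives the wrong ordering of patients. It should be fixed because it is a hepatic stopping rule in children. It does not bear on the primary endpoints.

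**What to change.** The sponsor's medical monitor should confirm the intended 4a limit and the central laboratory's INR normal limit. 4a should then be restated as an absolute level no higher than 4b's lowest stop level, that is, no higher than L + 0.4. One workable wording is: *INR above 1.5 after vitamin K, when baseline INR was normal*.

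A level of 1.5 sits above the 1.4 allowed at Cohort 2 entry and below 4b's lowest level (1.61 if L = 1.2; 1.51 if L = 1.1), so the levels run in order: 1.5, then 1.61–1.80. It corresponds to a rise of 1.5 − 1.2 = 0.3 to 1.5 − 0.9 = 0.6. Two limits should be known before adopting it:

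- The ordering needs L + 0.4 ≥ 1.5, so L of at least 1.1. At L = 1.0 a step of 0.1 remains, against 1.1 now.
- A child at the top of the normal range is stopped after a smaller rise than 4b asks for (0.3 against 0.4 at baseline 1.2). If an age-specific normal limit were as high as 1.4, a rise of just over 0.1 would suffice, and a higher level within L + 0.4 would be preferable.

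The cost is amendment wording and a memo to sites, with no change to INR sampling. The downside is somewhat more interruptions among patients with a normal baseline. The document gives no figure from which to estimate how many, but they are confined to rises that persist after vitamin K.
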